## **6.5 Loss to Follow-up**

To avoid participants being lost to follow-up, participants will be reminded by email or text message within a few days before scheduled visit. In the event of a missed visit, participants will be contacted by phone, email, or text message the next business day following the missed visit. Any participant who fails to attend the final study visit will be classified as lost to follow-up. In addition, a participant who cannot be located or fails to respond after three attempted contacts and has missed two consecutive visits (other than those scheduled primarily to provide stool samples) will be considered lost to follow-up. Efforts to contact the participant will be documented in source documents. There will be no replacement of participants who are lost to follow-up.

## **6.6 Use of Concomitant Medications During the Study**

Prior to study start, participants will be encouraged to receive Coronavirus Disease 2019 (COVID-19) vaccines, and receipt of COVID-19 vaccine prior to study will be reported in the Concomitant Medication CRF. At each study visit, the investigator will ask whether the participant has taken any prescription or over the counter medication since the last visit.

Any medication (includes vaccines not administered as part of study) administered to a participant at any time between the Day 1 visit and 28 days following each study vaccination during the study period must be recorded on source documents and the CRF with generic and/or trade name, indication, dosage, regimen, route of administration, and start and end dates. Between the end of these periods and the final study visits only concomitant medications associated with an SAE need to be recorded in the CRF.

The following concomitant medications/vaccinations are prohibited during the study; however, they must not be withheld by the treating physician if clinically indicated to treat a participant (e.g., response to epidemic, or post-exposure tetanus or rabies vaccine prophylaxis):

- Any investigational drug or vaccine throughout the duration of the study
- Any immunosuppressant or immune-modifying drug (includes systemic steroids) throughout the duration of the study
- Any immunoglobulin or blood product through study Day 57
- Any vaccine other than the study vaccines through study Day 57, which are prohibited for 30 days prior to or following each study vaccination (except for seasonal inactivated influenza and COVID-19 vaccines, which are prohibited for only 14 days prior to or following each study vaccination)
- Any intramuscular injection (except seasonal inactivated influenza and COVID-19 vaccines which are prohibited for only 14 days prior to or following each study vaccination) for 30 days prior to or following each study vaccination

Note: Medication (e.g., antipyretic) should not be recommended prophylactically prior to study vaccine administration to prevent the onset of any post study vaccine administration symptoms, although may be administered after study vaccine administration as clinically indicated.

Use of any prohibited medication must be recorded in the CRF and as such participant's inclusion in the Per Protocol Population will be evaluated on a case by case basis.

## **6.7 Emergency Unblinding**

In the event of a medical emergency, the investigator may request that the blind be broken for the participant experiencing the emergency if knowledge of the participant's study vaccine assignment may influence the participant's clinical care. Prior to unblinding, the investigator is encouraged (to the extent possible, without jeopardizing the participant's health) to contact the study medical monitor to discuss the decision to break the blind. Unblinding will occur through the secure interactive web response system (IWRS), to which there will be 24-hour access. Documentation of the unblinding event will be captured by the IWRS. The investigator will be expected to provide the rationale for the necessity of unblinding based on the reasonable expectation that knowledge of the participant's treatment assignment will have a meaningful impact on the participant's medical care in the short term. If a participant's treatment assignment is unblinded, the participant will remain in the study and continue with protocol-defined follow-up evaluations, including provision of biological samples, but will not receive further study vaccinations. The decision to unblind will be recorded in the participant's study record and communicated to the IRB/IEC and other regulatory bodies, as required.

## **6.8 Management of Birth Control and Pregnancy During Study**

Contraception status is assessed and documented prior to enrollment and each study visit for female participants who are of childbearing potential. Prior to enrollment and at each vaccination visit, staff will ask volunteers to confirm their use of adequate contraception methods if they are able to become pregnant and remind participants about the need to continue using adequate contraception consistently for at least 90 days after the last study vaccination and until cessation of vaccine virus shedding is confirmed. If a female participant becomes pregnant following randomization, no further study vaccines will be administered to that participant, and she will be encouraged to complete remaining visits and study procedures unless medically contraindicated. The investigator is required to notify Emmes within 24 hours of knowledge of a pregnancy. Any participant who becomes pregnant during the period between first vaccination and the last study visit will continue to be followed for pregnancy outcome, even if birth occurs after the scheduled end of the study for the participant, if possible. The pregnancy and its outcome will be reported on the Pregnancy CRF.

## **6.9 Clinical Assessments**

### **Vital Signs (VS)**

- For vaccination visits, the site must measure oral temperature in degrees Celsius or Fahrenheit (recorded to the nearest 0.1 degree) using the same thermometer that will be used subsequently by the participant to measure oral temperature during the post-vaccination period for assessing reactogenicity. For all non-vaccination visits, sites may record temperature using any route (aural, axillary, tympanic, temporal, etc.), and document the method used.
- Respiratory rate will be recorded in breaths per minute.
- Pulse rate in beats per minute will be measured by automated device or manually.
- Non-invasive systolic and diastolic blood pressure will be measured in millimeters of mercury (Hg) by automated device or manually.
- Vital signs will be taken during all targeted physical exams

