# 8 SAFETY ASSESSMENT AND REPORTING

## 8.1 Definitions

### 8.1.1 Adverse Event (AE)

An adverse event (AE) is any untoward medical occurrence in a participant after administration of the study vaccine and that does not necessarily have a causal relationship with the study vaccine. An AE can therefore be any unfavorable and unintended sign (including clinically significant abnormal laboratory finding), symptom, physical examination, or disease temporally associated with the use of the study vaccine, whether or not related to the study vaccine. This definition includes exacerbations of pre-existing conditions. Stable pre-existing conditions that do not change in nature or severity during the study are not considered AEs; however, these should be reported as part of the medical history.

**Solicited AEs** are pre-specific AEs that are common or known to be associated with vaccination that are actively monitored as potential indicators of vaccine reactogenicity. Investigators will not be required to

assess causality of solicited AEs if the onset is during the solicitation periods. Solicited AEs with onset after the solicitation period will be captured as unsolicited AEs.

For this trial, solicited AEs will be assessed on the day of study vaccination and for the 6 following days after each dose of study vaccine. Participants will be provided a memory aid to record the presence and severity or absence of solicited AEs. The memory aid may be accessed by smartphone or any device that connects to the internet. Solicited AEs with onset during the solicitation period that persist beyond the solicitation period will continue to be captured as solicited AEs.

The following specific solicited AEs will be monitored for this trial (Cohort 1):

- Fever (oral temperature  $\geq 38.0^{\circ}\text{C}$  or  $100.4^{\circ}\text{F}$ ). (The temperature comparison table with the different methods used can be found in the study MOP.)
- Chills
- Fatigue
- Headache
- Muscle aches/Myalgias
- Joint aches/Arthralgias
- Nausea
- Vomiting
- Abdominal pain
- Diarrhea

The following specific solicited AEs will be monitored for this trial (F Cohorts 2 and 3):

- Fever (axillary temperature  $\geq 37.5^{\circ}\text{C}$ )
- Vomiting
- Diarrhea
- Irritability
- Decreased feeding
- Decreased activity

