**Table 4: Grading scale to grade the severity of solicited AEs**

Solicited AE	Grade	Definition
Fever (oral body temperature)	0	< 100.4°F (none)
	1	≥ 100.4°F to < 101.5°F
	2	≥ 101.5°F to < 102.7°F
	3	≥ 102.7°F

Diarrhea	0	None
	1	2 to 3 loose stools per 24 hours
	2	4 to 5 stools per 24 hours
	3	6 or more watery stools per 24 hours
Chills or fatigue or headache or myalgias or arthralgias or nausea or vomiting or abdominal pain	0	None
	1	Causes no or minimal interference with usual social & functional activities
	2	Causes greater than minimal interference with but does not prevent usual social & functional activities
	3	Causes inability to perform usual social & functional activities

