#### **11.5.5.4 Other Safety Measures**

Vital signs will be summarized descriptively, including change from baseline for continuous measures. Vital sign abnormalities will be summarized descriptively.

Abnormal findings in physical examination will be summarized descriptively.

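### Site temperature may be taken by a different route after Day 1, while the planned change from baseline names neither the vital-sign baseline nor a rule for route

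*Protocol*

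**What the plan says.** Section 6.9 (Vital Signs) sets two rules. At vaccination visits: "For vaccination visits, the site must measure oral temperature in degrees Celsius or Fahrenheit", using the thermometer that the participant then takes home. At all other visits: "For all non-vaccination visits, sites may record temperature using any route (aural, axillary, tympanic, temporal, etc.), and document the method used". Screening is a non-vaccination visit, so the second rule covers it too.

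Section 11.5.5.4 plans the analysis: "Vital signs will be summarized descriptively, including change from baseline for continuous measures", and "Vital sign abnormalities will be summarized descriptively". It does not mention route.

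The vital-sign baseline is not named. Section 6.2.1 places baseline data in the screening period. Section 6.2.2 names Day 1 as baseline for the safety laboratory tests only.

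Fever is defined in several places. Table 4 grades "Fever (oral body temperature") only. Section 8.1.1 has one solicited-event list with an oral cut-off of 38.0 °C, and a second list, labelled for Cohorts 2 and 3, that begins "Fever (axillary temperature" and uses 37.5 °C. Section 8.1.1 also refers to a table comparing thermometry methods in the study's manual of procedures, which is not shown.

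**The concern.** A change from baseline is meant to show what happened to the participant. If the first reading is oral and the second comes from another site of the body, the difference also contains whatever systematic gap lies between the two routes. A lower-reading route would produce an apparent fall in temperature after vaccination and could mask a real rise. A higher-reading route would do the reverse. The same applies to a count of abnormal temperatures if a single threshold is applied to every route.

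Part of this is fixed at collection. Because the method must be documented, an analysis plan can separate or exclude readings by route, but it cannot supply an oral value that was never taken. Section 6.9 already protects like-for-like thermometry at vaccination visits, and the relaxation at other visits sits badly with the summary planned in section 11.5.5.4.

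**Working it through.** **Step 1. Which comparisons can cross routes, taking Day 1 as baseline (an assumption, since the protocol does not say so).**

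| Visit | Cohorts 1 and 3 | Cohorts 2 and 4 |
|---|---|---|
| Day 1 | oral (dose 1) | oral (dose 1) |
| Day 8 | any route, if an examination is prompted | any route, if an examination is prompted |
| Day 29 | any route, if an examination is prompted | oral (dose 2), scheduled for all |
| Day 36, Day 57 | no clinic visit | any route, if an examination is prompted |
| Unscheduled, or called in after the Day 169 telephone contact | any route, if examined | any route, if examined |

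The sources are sections 6.2.2 to 6.2.8, section 6.9 and Appendix 1. At the non-vaccination follow-up visits vital signs are part of a targeted examination, done only when a symptom or adverse event is reported. The examination on early withdrawal in section 6.4 is the other occasion. The only scheduled vital signs after Day 1 are therefore at Day 29 in Cohorts 2 and 4, and that comparison is oral to oral. In Cohorts 1 and 3 no comparison is protected.

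If screening were the baseline instead, the baseline itself could be any route, and even the Day 29 comparison in Cohorts 2 and 4 could cross routes.

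**Step 2. The only between-route figure in the document.** The two fever cut-offs in section 8.1.1 give 38.0 - 37.5 = 0.5 °C (0.9 °F). This concerns the axillary route only. Nothing is given for aural, tympanic or temporal readings.

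**Step 3. Illustrative shift in the mean change.** Assume that 0.5 °C is the oral-to-axillary offset and let q be the share of post-baseline readings taken in the axilla, the rest being oral. Shift = -0.5 × q.

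| q | Shift in mean change (°C) |
|---|---|
| 0% | 0 |
| 10% | -0.05 |
| 25% | -0.125 |
| 50% | -0.25 |
| 100% | -0.50 |

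The protocol gives no value for q, so only the range can be stated.

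**Step 4. Scale.** Grade 1 fever in Table 4 runs from 100.4 °F to below 101.5 °F, that is 38.0 °C to below 38.61 °C, a width of 0.61 °C. The illustrative offset is 0.5 / 0.61 = 82% of that band.

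**Step 5. Between arms.** Distortion of the nOPV minus mOPV difference = -0.5 × (q in nOPV - q in mOPV). With equal shares it is 0. With 60% and 40% it is -0.5 × 0.20 = -0.10 °C. The document gives no reason to expect unequal shares.

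**The case against.** The strongest reply is that this is detail for the statistical analysis plan. Section 11.5.1 leaves the full description of summaries to it, the route must be recorded, and a method comparison table exists, so mixing routes is possible but not prescribed. That stands for the handling of recorded readings. It does not stand for collection, because a missing oral value cannot be restored later.

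Second, few readings are affected. This also stands: follow-up vital signs are sporadic and mainly symptom-driven, and the one scheduled follow-up measurement is oral.

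Third, a reader might take 0.5 °C as the protocol's own offset between routes. The text does not support that. The axillary cut-off appears only in a list with irritability and decreased feeding, in a trial of adults aged 18 to 45. That list conflicts with the other list in section 8.1.1, with Table 4 and with the solicited events in section 13.6. The figure can illustrate, not measure.

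Fourth, a reader might infer that low-grade fever would be missed in the primary solicited-event endpoint. That is not shown either. Participants record solicited events themselves and measure oral temperature at home, graded on an oral scale. The solicited windows are Days 1 to 7 and 29 to 35, so the Day 8 and Day 36 visits fall after them. An unscheduled visit could fall inside, but the participant's own recording continues then. No passage says that a non-oral site reading is judged against the oral cut-off.

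Fifth, a reader might infer bias between vaccine and control. Randomisation is blocked and stratified by site (section 11.2), and the unblinded staff who give the vaccine take no part in assessments (section 5.2). If route is a matter of site practice, it should be balanced between arms.

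**Conclusion.** The point holds in a narrow form. Sections 6.9 and 11.5.5.4 together permit a temperature change from baseline computed across routes, and the vital-sign baseline is undefined. With a Day 1 baseline this reaches every later site temperature in Cohorts 1 and 3, and those at Day 8, Day 36, Day 57 and unscheduled examinations in Cohorts 2 and 4.

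The size is unknown. The range of 0 to -0.5 °C rests on two assumptions: that the gap between the printed cut-offs equals the route offset, and that non-oral readings are axillary. The first rests on text that is itself in conflict.

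It would be too strong to say that the protocol fixes baseline as oral, that all later visits are affected, or that the primary fever endpoint or the comparison of arms is biased. What remains is an avoidable artefact in a descriptive safety summary: worth correcting because correction is nearly free, and not a threat to the trial's conclusions.

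**What to change.** In section 6.9, have sites take temperature orally at in-person follow-up and unscheduled visits where feasible, recording the route when another is used. A site oral thermometer is enough, and participants need not bring theirs back.

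In section 11.5.5.4, name Day 1 as the vital-sign baseline, compute temperature change only where both readings are oral, apply the same restriction to temperature abnormalities, and list non-oral readings with their route.

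Separately, reconcile the two solicited-event lists in section 8.1.1, including their fever definitions, with Table 4 and section 13.6.

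The cost is about one sentence in each of sections 6.9 and 11.5.5.4, with no added visit or procedure. The downside is that a few non-oral readings move from the summary table to a listing.

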### **Height and Weight**

- Height will be measured and recorded to the nearest centimeter (cm).

- Weight will be measured in kilogram (kg) and recorded to the nearest 0.1 kg.

### **Physical Examination**

Complete physical examination will include assessment of vital signs, head, eyes, ears, nose, oropharynx, neck, respiratory/pulmonary, cardiovascular, abdomen, musculoskeletal, lymph nodes (neck, supraclavicular, axillary, inguinal), extremities, skin, and neurological.

### **Targeted Physical Examination**

A focused physical examination based on any interim symptoms/AEs reported by the participant. Whenever required, to always include an assessment of vital signs.

### **Medical History**

A comprehensive medical history will be collected at screening, including details of any previous vaccinations in the past 30 days, any history of reactions to vaccinations, participation in clinical trials (especially clinical trials of vaccines), prior surgery or hospitalization, allergy to food/drugs, current medication and history of any chronic or recurrent medical conditions. Detailed poliovirus vaccination history to be collected, including requests to review poliovirus vaccination records. If records not obtainable, to ascertain if vaccination history can be reasonably established by history of lifelong residency locations and polio vaccines that were available for routine immunizations at the relevant time periods in these locations.

## **7 LABORATORY EVALUATIONS/REQUIREMENTS**

### **7.1 Sample Collection, Distribution and Storage**

Blood samples to evaluate vaccine safety will be obtained and processed at the clinical trial site and transported to each site's designated laboratory for clinical testing.

Serum specimens collected for assessment of immunogenicity will be separated into aliquots per study specific process and stored at  $\leq 20^{\circ}\text{C}$  before being shipped to the Polio and Picornavirus Laboratory Branch at the United States Centers for Disease Control and Prevention (CDC). For screening purposes (eligibility determination) only, a sample will be shipped to a commercial qualified laboratory, Quest Diagnostics. Samples will be stored in controlled-temperature freezers, with backup power supply to assure proper sample storage.

Stool samples to assess presence of poliovirus and genetic stability of shed virus will be processed at the clinical trial site in a Biosafety Level 2 (BSL-2) laboratory and stored at  $\leq 20^{\circ}\text{C}$  before being transported to the Polio and Picornavirus Laboratory Branch at the CDC or Viroclinics Biosciences B.V., Rotterdam, The Netherlands.

After either reference laboratory (CDC or Viroclinics) completes a successful test on any serum or stool sample that has a back-up sample in storage, the laboratory will destroy any of the remaining sample used for the testing within six months.

Details as to how blood and stool specimens should be collected, processed, aliquoted, labeled, stored, and shipped will be provided in the study-specific Laboratory Manual.

## 7.2 Clinical Laboratory Tests

Protocol mandated clinical screening and safety laboratory tests will be conducted in real time by site local laboratories that are properly accredited and subscribed to a proficiency testing program. These tests include:

- CBC: hemoglobin, hematocrit, WBC count, neutrophil count, lymphocyte count, eosinophil count, and platelet count, performed at screening, and at Day 1 and Day 8 visits
- Serum Chemistry: ALT, total bilirubin, and creatinine, performed at screening, and at Day 1 and Day 8 visits
- Pregnancy test: Serum  $\beta$ -HCG at screening, then urine  $\beta$ -HCG prior to each study vaccination (conducted on site)
- Human immunodeficiency viruses 1 and 2 (HIV 1/2) infection testing performed at screening
- Hepatitis B virus surface antigen performed at screening (HBsAg)
- Hepatitis C virus antibody (HCV Ab), if positive, HCV PCR, performed at screening
- Total IgG and IgA performed at screening

Laboratory results will be reviewed promptly by the investigator. Participants will be notified of any clinically significant abnormalities. If clinically significant abnormalities are identified during screening, participants will be referred to their primary health provider or appropriate medical center. If identified during the study, participants may be asked to return to the study site for further evaluation, including clinical evaluation and repeat laboratory testing (e.g., monitoring for resolution or stabilization) as warranted. Any test may be repeated for test results determined to be spurious by the investigator (e.g., following improper specimen collection) or if a valid test cannot be performed on the original blood collected (e.g., collection tube broken during transportation).

The immunological assays to be performed include:

- Serum neutralizing antibodies to type-specific polioviruses at screening and 28 days after each vaccine dose, to be performed at the Polio and Picornavirus Laboratory Branch at the CDC (for screening purposes [eligibility determination] only, baseline assays will be performed at a commercial qualified laboratory, Quest Diagnostics)

## 7.3 Assessment of Shed Poliovirus

- Multiplex real-time PCR for identification of type-specific poliovirus in stool, to be performed at the Polio and Picornavirus Laboratory Branch at the CDC
- CCID50 for quantification of type 1 or 3 poliovirus in stool, to be performed at the Polio and Picornavirus Laboratory Branch at the CDC
- Quantitative PCR for quantification of type 1 or 3 poliovirus in stool may be performed at Viroclinics Biosciences B.V.
- Neurovirulence of fecally shed vaccine virus as assessed by a transgenic mouse neurovirulence test (TgmNVT), to be performed at Viroclinics Biosciences B.V.
- NGS of fecally shed vaccine virus, to be performed by Viroclinics Biosciences B.V.

The operational definition of cessation of vaccine virus shedding in stool is 2 consecutive stool specimens determined to be negative by PCR obtained over a period no shorter than 24 hours.

